Clinical Efficacy Analysis of Resveratrol in the Treatment of Primary Ovarian Insufficiency

Date: May 16, 2022

Research Proposal Summary

Statistical analysis

The case observation form completed by the test center was reviewed and returned by the project team of Reproductive Medicine Center, Affiliated Hospital of Nantong University, and the data was processed by a statistical analyst. The data in the case report form is entered in two copies, and the database is locked after verification and confirmation. SPSS26.0 software was used for statistical analysis. The full analysis set (FAS) and the per-protocol set (PPS) were used for effectiveness analysis, and the safety data set (SS) was used for safety analysis. Measurement data were expressed as mean±standard deviation ($\bar{x}\pm s$), multiple time points were compared by repeated measures analysis of variance, and pairwise comparisons were by Bonferroni test; enumeration data were expressed by the number of cases or percentages, and χ^2 was used. Test for statistical comparison. $P<0.05$ indicated that the difference was statistically significant.

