	
have participated in other clinical trials within the past three months;
 
8. Patients with suspected or real history of alcohol and drug abuse;
 
9. Known allergy to the investigational drug or its components;
 
10. Other patients deemed unsuitable for participation in this trial by the investigator.
 
Note: Patients who were receiving hormone replacement therapy at the time of recruitment were required to take at least a 3-month suspension of medication to participate in this trial.

Trial grouping and medication
	
1. POI patients group: According to the computer-generated random sequence, eligible patients were randomly assigned to the RES group and non-RES group according to 1: 1. POI IVF patients were divided into two groups: the RES treatment group (group A) and the non-RES treatment group (group B). Basal sex hormone and anti-Muller tube hormone were administered on day 2/3 of the menstrual cycle before treatment and 3 months after treatment. Antral Follicle (AFC) was detected by transvaginal B-ultrasonography, and basic sex hormones included follicle-stimulating hormone (FSH), Luteinizing hormone (LH), Estradiol 2 (E₂) and Testosterone (T).
 
2. Medication: Patients in group A received oral RES at 250mg daily for three months, and those in the non-RES group received oral vitamin E at 100mg daily for three months.

Treatment and follow-up
	
Course of treatment: Patients in group A received oral RES at 250mg daily for three months, and those in the non-RES group received oral vitamin E at 100mg daily for three months. All patients used microstimulation to superstimulate ovulation, and

clomiphene 50-150mg was taken orally from the 3rd to 5th day of menstruation, once a day for a total of 5 days later, the sex hormones and follicular diameter were checked, and 150-300IU Gonadotropin (Gn) was added as appropriate to the night needle day. After follicle maturation, 10000IU of Human Chorionic Gonadotropin (HCG) was injected intramuscularly or 250ug Ovidrel subcutaneously to induce ovulation. 36-38 hours later, a vaginal ultrasound-guided puncture was performed to collect eggs.

Specific inspection items include:

1. The patient's hormone levels (basal FSH, LH, E2, T) were detected on day 2/3 of the menstrual cycle;
2. Anti-Mullerian hormone (AMH) was detected in patients on day 2/3 of the menstrual cycle;
3. The numbers of antral follicles (AFC) were recorded by B ultrasound transvaginal;

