4. Pregnancy was recorded at the outpatient follow-up for patients with reproductive needs ;
5. Patients were routinely tested for blood routine (RBC, WBC, PLT, HGB), liver function (ALT, AST) and renal function (BUN, Cr), and recorded adverse events.

Note:

1. Basal follicle-stimulating hormone (FSH) $\geq 10\text{mIU/ml}$ at the first visit, and if other inclusion criteria are met if the patient has a history of testing with a baseline FSH $\geq 10\text{mIU/ml}$ in the past (interval > 4 weeks), he or she can be included in this study and drug therapy can be started; (Interval > 4 weeks) If the basic FSH $\geq 10\text{mIU/ml}$ has not been diagnosed, the patient is required to visit the hospital again after 4 weeks. If the basic FSH is still $\geq 10\text{mIU/ml}$, they can be included in this study and drug therapy

	
can be started.
 
2. For patients with regular menstrual periods, the basal FSH and antral follicle count (AFC) should be followed up on the 2nd to 4th day of the menstrual cycle. If the patient has menstrual cramps after the follow-up and has not exceeded the visit window, they are required to re-examine on the 2nd to 4th day of the menstrual cycle and record the examination data.

Study endpoint	
Primary endpoint : FSH, LH
 
Secondary endpoints :
 
(1) FSH, LH, E₂, T; (2) Antral follicle count (AFC); (3) Basal sex hormones and Anti- Mullerian hormone (AMH) on day 2/3 of the menstrual cycle; (4) Embryo laboratory indicators including number of eggs harvested, number of MII eggs, normally fertilized number, and number of good quality embryos; (5) Peripheral blood human villous gonadotropin (HCG); (6) Clinical pregnancy rate (patients with reproductive needs).

Security indicators	
1. Blood routine (RBC, WBC, PLT, HGB) , liver function (ALT, AST) and renal function (BUN, Cr) ;
 
2. Patient adverse events were recorded.

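### FAS and PPS both serve the efficacy analysis with neither ranked, and repeated measures ANOVA without a missing-data rule turns the FAS result for FSH and LH into a completer analysis

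*SAP*

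**What the plan says.** The SAP's Statistical analysis section is a single paragraph. On analysis sets it says "The full analysis set (FAS) and the per-protocol set (PPS) were used for effectiveness analysis". It defines neither set, does not label one primary or supportive, and does not say what happens if they disagree. One significance threshold, 0.05, applies throughout.

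For continuous outcomes, "multiple time points were compared by repeated measures analysis of variance" and "pairwise comparisons were by Bonferroni test". The Bonferroni step concerns pairwise comparisons, not the choice of analysis set. On software, "SPSS26.0 software was used for statistical analysis". Categorical outcomes are handled by chi-square. There is no rule for missing values.

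In the Protocol summary, the Study endpoint row reads "Primary endpoint : FSH, LH". The Trial grouping and medication row schedules the hormone measurements "before treatment and 3 months after treatment", so the primary comparison has two time points.

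**The concern.** Two features of the plan act on the same result.

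- **No precedence.** Two analysts could both follow this SAP, obtain a significant result in one set and not in the other, and reach opposite conclusions. Nothing in the text says which of them is right.
- **Completers only.** Classical repeated measures ANOVA needs a value at every time point, and the SPSS repeated-measures procedure drops incomplete cases listwise. With two time points, a patient who lacks the 3-month FSH or LH leaves that test. The full set is then full in name only.

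Missing 3-month values may not be random here. Eligibility requires at least 4 months of amenorrhea or oligomenorrhea, yet basal hormones are drawn on cycle day 2/3. The second note under Treatment and follow-up gives a sampling window for women with regular periods only. A woman who conceives before month 3 has no basal sample. Whether a value exists may therefore depend on ovarian function, which is what the treatment is meant to change.

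**Working it through.** **Inputs from the documents.** 150 patients, 1:1 allocation (75 per arm), threshold 0.05 (taken as two-sided), two time points. The documents give no power, effect size, SD, dropout rate or set definitions, so 150 cannot be reproduced. The values below that are marked as assumed show a range.

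**1. Orientation.** With 75 per arm, the difference detectable with 80% power is (1.96 + 0.84) × √(2/75) = 0.46 SD of the analysed quantity. This is a reference point, not a figure from the plan.

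**2. Choice of set, one endpoint.** For nested sets with exclusion unrelated to outcome, the two test statistics have correlation √(n_PPS/n_FAS). The chance that at least one exceeds 1.96 in absolute value under no effect is:

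| PPS as share of FAS (assumed) | Correlation | Success on either | Success on both required |
|---|---|---|---|
| 80% | 0.894 | 7.1% | 2.9% |
| 90% | 0.949 | 6.5% | 3.5% |
| 95% | 0.975 | 6.0% | 4.0% |

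The last column is 10% minus the third, since P(both) = 5% + 5% − P(either).

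**3. Random missingness.** If 15% lack the 3-month value (assumed), 75 × 0.85 ≈ 64 per arm remain. The detectable difference becomes 2.80 × √(2/64) = 0.50 SD. Power at 0.46 SD falls from 80% to 73%. Type I error does not move: simulation of the group-by-time test (with two time points, a t-test on change) on completers gave 0.047 at 10% missing and 0.051 at 20%.

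**4. Informative missingness in one arm.** The simulation had no true effect, 75 per arm and an assumed baseline-to-3-month correlation of 0.6. In one arm only, patients with a poorer change were more likely to be missing (log-odds slope 1 per SD of change, assumed):

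| Nominal dropout | Type I error, completers | Bias (baseline SD) |
|---|---|---|
| 10% | 0.11 | −0.11 |
| 20% | 0.20 | −0.18 |
| 30% | 0.30 | −0.25 |

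**5. What a better model recovers.** With common variance and baseline correlation r, the change score has variance proportional to 2(1 − r) and the baseline-adjusted outcome to 1 − r². Their ratio is (1 + r)/2. An effect of 0.46 SD of change therefore becomes 0.46/√((1 + r)/2) after adjustment:

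- r = 0.5: 0.46/√0.75 = 0.53; power with 64 per arm about 85%.
- r = 0.6: 0.46/√0.80 = 0.51; about 82%.
- r = 0.7: 0.46/√0.85 = 0.50; about 80%.

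These compare with 73% for the completer change analysis. Baseline adjustment also removes bias from dropout that depends on baseline in one arm. An unconstrained mixed model, with separate baseline means by arm, does much less: about 76% power against 74-75% for completers in simulation at 15% random missingness. With one-arm dropout driven by change (15-20% nominal), it removed only about 15-25% of the bias.

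**The case against.** Several points on the other side stand.

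- **The SAP does not say that success on either set suffices.** A reader might infer two chances to win, but the text is silent. If both sets had to agree, the rule would be conservative (2.9-3.5%). The 6.5-7.1% is therefore conditional.
- **The two features partly offset each other.** The more the FAS shrinks towards completers, the closer it lies to the PPS and the smaller the inflation: 6.0% at 95% overlap.
- **A four-test figure would mislead.** Counting FSH and LH in both sets gives about 11-13% (assumed correlation 0.3-0.6). FSH and LH on the FAS alone already give about 9%. Most of that inflation comes from having two primary endpoints, a separate issue that ranking the sets does not address.
- **Case deletion is inferred, not stated.** The SAP prescribes no deletion rule and names no SPSS procedure. An unstated imputation step would avoid the loss. Chi-square outcomes such as clinical pregnancy are not affected by this mechanism.
- **Bias in a particular direction is not shown.** A reader might infer that outcome-related dropout must bias both sets the same way. The documents do not support that: distortion of the between-arm contrast generally needs missingness that also differs by arm, and its direction depends on who is missing.

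None of this supplies the missing precedence. Nor does it change the fact that the named method, as written and with no imputation rule, cannot use a patient who has only a baseline value.

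**Conclusion.** The point holds, at moderate size, and should be settled before the database is locked. The missing precedence is read directly from the SAP. The reduction to completers follows from the named method, two time points and the absence of a missing-data rule.

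Set choice alone adds about 1.5-2 percentage points per endpoint, if success on either set is accepted and the PPS is 80-90% of the FAS. Random loss of 15% costs about 7 points of power at 0.46 SD and leaves type I error alone. The larger risk is selective completion that differs by arm. Under the assumed mechanism above, completer type I error reaches 0.11 at 10% nominal dropout and 0.30 at 30%. Those rates show what could happen; the documents do not show that such dropout will occur.

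**What to change.** Amend the SAP's Statistical analysis section as follows.

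1. Define both sets. Make the FAS (all randomised patients, as allocated) the sole basis for the efficacy conclusion, and call the PPS supportive.
2. For FSH, LH and the other repeated continuous outcomes, replace repeated measures ANOVA with a likelihood-based mixed model in SPSS MIXED. It should use every available baseline and 3-month value and constrain the arms to a common baseline mean (time and treatment-by-time terms with no baseline treatment difference, which is equivalent to adjusting for baseline). The constraint matters: without it, two time points leave little to recover.
3. Add one prespecified sensitivity analysis for informative missing 3-month values, for example under an assumption less favourable to RES. Treat patients who conceive separately. Imputing them as poor responders would score a favourable outcome, and one of the trial's own secondary endpoints, as a failure.

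The cost is a few sentences and slightly more analysis in software already named, with no change to recruitment, visits or treatment. The model does not by itself cure informative dropout, which is why the third item is needed. Multiplicity across FSH and LH needs its own rule.

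### With no separate safety method, the laboratory safety tests default to a comparison of means, which can leave one to three patients per arm with marked rises unseen

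*SAP*

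**What the plan says.** The protocol's Security indicators row lists blood counts, "liver function (ALT, AST) and renal function (BUN, Cr"), and a second item: "Patient adverse events were recorded". Item 5 of the inspection items under Treatment and follow-up names the same tests alongside adverse events. All eight laboratory variables are continuous.

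The SAP's Statistical analysis paragraph assigns a population, "the safety data set (SS) was used for safety analysis", but no method specific to safety. Its general rules are:

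- Continuous data: "Measurement data were expressed as mean±standard deviation", and "multiple time points were compared by repeated measures analysis of variance", with Bonferroni pairwise comparisons.
- Categorical data: "enumeration data were expressed by the number of cases or percentages", compared by chi-square.
- Significance: P below 0.05.

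Neither document gives a reference range, a multiple of the upper limit of normal (ULN), a toxicity grade, a shift table, a worst post-baseline value or a listing of patients with abnormal results. Neither states when the safety samples are drawn.

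**The concern.** Safety chemistry is collected largely so that a marked abnormality in an individual patient is noticed. A mean with its SD, and an ANOVA on means, answer a different question: whether the arm as a whole has shifted. A handful of large values moves the mean little and inflates the SD, which weakens the test.

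The trial could therefore report no significant difference in ALT, AST or Cr while a few patients in one arm had marked rises that no planned table shows. That statement about means would be true, but incomplete as a safety summary.

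**Working it through.** **Inputs from the documents.** 150 patients randomised 1:1, so 150/2 = 75 per arm if all contribute laboratory values; significance at P<0.05 (sidedness not stated, two-sided assumed). The documents give no laboratory SD, threshold or expected abnormality rate, so there is no stated figure to reproduce.

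**Assumptions for illustration.** ALT mean 20, SD 8 U/L in unaffected patients; k resveratrol patients at 150 U/L and none in control; a two-sample t-test standing in for the between-arm contrast. With two groups and two time points, the group-by-time test of repeated-measures ANOVA equals a t-test on change.

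**Step 1: shift and SD.**

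- Mean shift = k × (150 − 20)/75. For k = 3: 3 × 130/75 = 5.2 U/L.
- With p = k/75, variance = [(1 − p) × 8² + p(1 − p) × 130²] × 75/74. For k = 3: (61.4 + 649.0) × 75/74 = 720, so the SD is about 26.8, against 8 before.
- SE of the difference = √[(720 + 64)/75] = 3.23.
- Typical t = 5.2/3.23 = 1.61, against a critical value of 1.98 (148 df).

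| k of 75 | Mean shift (U/L) | SD | Typical t | Simulated share with P<0.05 |
|---|---|---|---|---|
| 0 | 0 | 8 | 0 | about 5% |
| 1 | 1.7 | 17.0 | 0.80 | 2.6% |
| 2 | 3.5 | 22.5 | 1.26 | about 7% |
| 3 | 5.2 | 26.8 | 1.61 | 18-19% |
| 4 | 6.9 | 30.4 | 1.91 | 42-43% |
| 5 | 8.7 | 33.6 | 2.18 | about 73% |

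**Step 2: why the miss stops at about three.** If k patients share a rise D that is very large relative to the ordinary SD, D cancels and t tends to √[k(n − 1)/(n − k)]. With n = 75:

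- k = 1: √(74/74) = 1.00
- k = 2: √(148/73) = 1.42
- k = 3: √(222/72) = 1.76
- k = 4: √(296/71) = 2.04

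Up to three patients the limit stays below 1.98 however large the rise. From four it exceeds it.

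**Step 3: sensitivity to the assumptions.** Share of simulated trials with a significant group-by-time test. ALT: lognormal, mean 20, SD 8, ULN 40, within-patient correlation 0.6. Cr: mean 60, SD 10 µmol/L, correlation 0.7. All of these are assumed.

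| Rise | k = 1 | k = 2 | k = 3 | k = 4 | k = 5 |
|---|---|---|---|---|---|
| ALT 3×ULN | 3% | 8% | 17% | 37% | 65% |
| ALT 5×ULN | 1.3% | 3.3% | 15% | 53% | 89% |
| ALT 8×ULN | 0% | 0.2% | 7% | 62% | 98% |
| Cr 2× mean | 5% | 10% | 16% | 26% | not run |
| Cr 3× mean | 3% | 7% | 19% | 42% | not run |

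For one to three patients, a larger ALT rise makes a significant result less likely. Two patients at 5×ULN move the arm mean only from 20 to about 25 U/L, well under the assumed ULN of 40.

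**Step 4: what counting adds.** Exact 95% CIs: 1/75 = 1.3% (0.03-7.2%), 2/75 = 2.7% (0.3-9.3%), 3/75 = 4.0% (0.8-11.2%). For 3 v 0, two-sided Fisher P = 2 × (75 × 74 × 73)/(150 × 149 × 148) = 0.24. For 4 v 0 it is 0.12 and for 5 v 0 it is 0.058. Uncorrected chi-square gives 0.08 for 3 v 0 and 0.043 for 4 v 0. Testing the counts is therefore not a route to significance; the benefit is that the cases appear.

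**The case against.** The strongest reply has four parts.

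- **Counts would not reach significance either.** This stands. At 3 v 0 Fisher gives P = 0.24, and at five patients the test of means is the more likely to flag a difference. Setting 19% power for means against a table that always shows three cases compares a test with a description. The case for counting rests on display alone.
- **Adverse events already provide a count.** This stands in part. They are recorded, and the SAP's categorical rule would tabulate them by arm. But no threshold or rule says when a laboratory value becomes an adverse event, and with four centres practice may differ.
- **The SAP never applies ANOVA to the laboratory tests by name.** This is true; the rule reaches them by default. If it was not meant to, no laboratory safety analysis is specified, and the same addition is needed.
- **Nothing irreversible happens.** This is also fair: tables can be made later from stored values. Limits chosen after the data are seen are less credible, however.

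A reader might infer that the trial's safety conclusion would be wrong. The documents do not support that: they state no safety hypothesis or conclusion, and no rule that a non-significant P value means safe. Nor do they show that organ injury always appears as isolated rises, and nothing here was calculated for blood counts.

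**Conclusion.** The concern holds as a reporting gap. As written, the plan gives no per-patient view of the laboratory safety data, and a comparison of means can leave about one to three patients per arm with marked ALT, AST or Cr rises unseen. At 75 per arm with assumed ALT of 20±8 U/L and rises to 150 U/L, the chance of P<0.05 is about 7% for two patients and 18-19% for three. Across the other assumed rises in ALT and Cr, three patients give 7-19%. AST and BUN were not simulated; the limiting argument in Step 2 applies to any test where the rise is large relative to its SD. By five patients at 150 U/L the comparison of means usually detects the shift.

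The consequence is a possibly incomplete and misleading safety statement. The efficacy endpoints are not affected. The change is worth making because it is cheap and should precede database lock.

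**What to change.** Add a short safety section to the SAP. For each laboratory test, in the safety set and by arm:

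- the number and percent of patients who move from normal at baseline to outside the local laboratory's reference range, and the number and percent who exceed a multiple of the upper limit that the sponsor fixes before database lock, each with an exact 95% CI;
- a shift table from baseline to worst post-baseline value;
- a listing of the patients so identified.

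Keep mean±SD as a supplement, and state that a non-significant P value is not to be read as evidence of safety. State whether and when a laboratory abnormality is recorded as an adverse event, so that the two tabulations can be reconciled, and state when the safety samples are taken, since the shift table needs a baseline value.

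Cost: SAP wording, a few extra tables, and reference ranges from the four centres. If baseline and follow-up samples are already being taken, no new measurement is needed. The change concerns reporting only and sets no rule for managing patients.

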Clinical Efficacy Analysis of Resveratrol in the Treatment of Primary Ovarian Insufficiency

Date: May 16, 2022

Research Proposal Summary

Scheme number	LCYJ-B05
Scheme name	Clinical effect of resveratrol on early onset ovarian insufficiency
Version number/date	Version 2.1, May 16, 2022
Indications	POI
Test purpose	In order to evaluate the role of resveratrol in the occurrence and development of a variety of ROS-related diseases including POI/POF, and to clarify the clinical effect and mechanism of resveratrol antioxidant therapy.
Research design	Prospective, multicenter, randomized, controlled clinical trial design
Total number of cases	150
Number of research centers	4
Study period	36 months
Research object	Diagnostic criteria : The diagnostic criteria for premature ovarian insufficiency (POI) refer to the “2017 Chinese Expert Consensus on Clinical Diagnosis and Treatment of Premature Ovarian Insufficiency” and “2016 Expert Consensus on Hormone Supplementation Therapy for Premature Ovarian

Insufficiency”; including: (1) Age <40 years old; (2) oligomenorrhea or amenorrhea for at least 4 months; (3) at least 2 times serum basal follicle-stimulating hormone (FSH) >25IU/L (interval > 4 weeks). Subclinical POI: FSH level is 15~25 IU/L, which is a high-risk group.

The diagnostic criteria for premature ovarian failure (POF) refer to the “2017 Chinese Expert Consensus on Clinical Diagnosis and Treatment of Premature Ovarian Insufficiency”, which refers to amenorrhea, FSH>40IU/L, and decreased estrogen levels before the age of 40, accompanied by varying degrees of perimenopause Stage symptoms are the terminal stage of POI.

standard constrain:

1. Amenorrhea or oligomenorrhea at least 4 months and two (>4 weeks interval) basal FSH \geq 10mIU/ml;
2. age<40 years old;
3. Informed consent, voluntary experiment.

Exclusion criteria:

1. Pregnant and lactating patients;
2. Patients with endometriosis, adenomyosis, endometrial lesions (submucosal fibroids ,endometrial polyps, etc.) , uterine fibroids>4 cm or hysterectomy;
3. Patients with adrenal cortical hyperplasia or tumor;
4. Ovarian neoplasms patients;
5. Hydrosalpinx patients;
6. Hyperprolactinemia patients;
7. Patients who are participating in other clinical trials or

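### The SAP plans arm summaries and a P value but no RES-minus-vitamin E estimate or confidence interval, so the trial would not quantify its treatment effect or show what a non-significant result leaves open

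*SAP*

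**What the plan says.** The SAP's Statistical analysis section is one paragraph. For continuous data it states "Measurement data were expressed as mean±standard deviation", and the analysis is that "multiple time points were compared by repeated measures analysis of variance, and pairwise comparisons were by Bonferroni test". For categorical data, "enumeration data were expressed by the number of cases or percentages", compared by a chi-square test. The one rule for reading results is that P below 0.05 "indicated that the difference was statistically significant".

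The Protocol summary gives "Total number of cases 150", with patients "randomly assigned to the RES group and non-RES group according to 1: 1" and vitamin E as the comparator. The Study endpoint row lists "Primary endpoint : FSH, LH". It places clinical pregnancy among the secondary endpoints and restricts it to patients with reproductive needs, without saying how many there will be.

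Neither document mentions a between-arm difference, a confidence interval, a target effect, a margin or power. Nothing suggests that such text was redacted or lost.

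**The concern.** The Protocol's stated purpose includes clarifying the clinical effect of resveratrol. Arm means with SDs and a significance verdict do not state how large that effect is or how precisely it is known. The gap matters whichever way the test falls:

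- If P<0.05, nothing planned says whether the change in FSH or LH is big enough to matter.
- If P≥0.05, nothing planned separates a resveratrol effect close to that of vitamin E from a trial too imprecise to tell.

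Both arms take a daily product for three months, and no margin or power statement is available to fall back on. For pregnancy and adverse events, where counts may be small, a P value alone says little about the range of compatible effects.

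**Working it through.** **Inputs from the documents.** Total 150 at 1:1, so 150/2 = 75 per arm. Significance level 0.05; sidedness is not stated, and two-sided is taken here. Hormones are measured before treatment and 3 months after it (Protocol, Trial grouping and medication).

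**Inputs assumed because the documents give none.** Hormone results are in SD units. Dropout is shown as 75 or 60 evaluable per arm. The within-patient correlation r is 0.3 to 0.7. Pregnancy counts are illustrative. The subset with reproductive needs is either everyone (75 per arm) or about half (37 per arm).

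**The plan's own figure.** The total of 150 cannot be reproduced, since no effect, SD, power or dropout is stated. Back-solving with n per arm = 2(z_α/2 + z_β)²/d²:

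- 80% power, d = 0.46 SD: 2(1.960 + 0.842)²/0.46² = 74.2, so 75.
- 90% power, d = 0.53 SD: 2(1.960 + 1.282)²/0.53² = 74.8, so 75.

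Neither effect size is the documents' own.

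**Hormone endpoint, one unadjusted post-treatment comparison.** Half-width = 1.96 × √(2/n) SD.

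- n = 75: 1.96 × 0.1633 = 0.320 SD.
- n = 60: 1.96 × 0.1826 = 0.358 SD.

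At P = 0.06, z = 1.881. With 75 per arm the estimate is 1.881 × 0.1633 = 0.307 SD and the interval is 0.307 ± 0.320, or −0.01 to 0.63 SD. Larger P values give lower upper limits: 0.53 SD at P = 0.2, 0.43 at P = 0.5 and 0.36 at P = 0.8.

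**Using the baseline, n = 75.** For a difference in change, multiply 0.320 by √(2(1−r)). For a baseline-adjusted difference, multiply it by √(1−r²).

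| r | Difference in change (SD) | Baseline-adjusted (SD) |
|---|---|---|
| 0.3 | 0.38 | 0.31 |
| 0.5 | 0.32 | 0.28 |
| 0.7 | 0.25 | 0.23 |

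**Pregnancy, Newcombe interval** (built from the Wilson limits of each arm).

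- 8/75 v 8/75: each arm 10.67% (Wilson 5.50 to 19.66). Half-width √(5.17² + 8.99²) = 10.4 points; P = 1.0.
- 12/75 v 6/75: 16.0% (9.40 to 25.92) v 8.0% (3.72 to 16.37). Difference 8.0 points. Lower limit 8.0 − √(6.60² + 8.37²) = −2.7; upper limit 8.0 + √(9.92² + 4.28²) = 18.8. Pearson P = 0.13.
- 4/37 v 4/37: each arm 10.81% (4.29 to 24.71). Half-width √(6.52² + 13.90²) = 15.4 points; P = 1.0.

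In the first example, a difference about the size of the 10.7% rate itself is not excluded, although P = 1.0. In the 37-per-arm case the interval is wider still.

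**The case against.** The strongest reply is that no harm is actually planned. A reader might infer that P≥0.05 would be read as no difference and that a wrong conclusion is therefore likely. The SAP does not say this: it defines what counts as significant, gives no rule for the opposite case, and neither document states an equivalence or non-inferiority aim. That part of the reply stands, and such a misreading is only a possibility the plan does nothing to prevent.

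A reader might also infer that large effects on FSH and LH would remain open. At full enrolment that is too strong. The 0.63 SD limit is close to the worst case for a non-significant unadjusted comparison, and an effect of 0.8 SD would be excluded. Moderate is the supportable word. Wide uncertainty relative to the rate is supportable for pregnancy, on assumed counts.

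The 0.32 SD figure is for a single unadjusted comparison, whereas the SAP names repeated measures analysis of variance. This is correct, and it is why the range over r is shown; the half-width stays between 0.23 and 0.38 SD.

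A reader of the results could rebuild an unadjusted difference and interval from arm means, SDs, counts and group sizes. This is true, and the omission biases no estimate. But an interval for change from baseline, or a baseline-adjusted one, cannot be recovered without the within-patient correlation.

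Finally, software may print differences and intervals alongside Bonferroni comparisons. Printing them is not a commitment to report them, and the SAP does not say whether the pairs are arms or time points.

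**Conclusion.** The point holds as an omission of prespecified effect estimates and confidence intervals, confirmed across both documents. It limits what the results can say; it does not invalidate the tests or the data collected. It should be corrected before analysis.

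With 75 per arm, the missing interval would be about ±0.32 SD for an unadjusted hormone comparison, ±0.25 to ±0.38 SD for a difference in change, and ±0.23 to ±0.31 SD with baseline adjustment. On the unadjusted figure, a result just short of significance leaves effects up to about 0.63 SD open. For pregnancy at a rate near 11%, it would be about ±10 points if all 75 per arm count and about ±15 points if 37 do.

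These sizes rest on full enrolment (except the 60-per-arm figure), two-sided 95% intervals, correlations of 0.3 to 0.7, and assumed pregnancy counts and subset size. The omission itself depends on none of them.

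**What to change.** Replace the reporting sentence in the SAP's Statistical analysis section so that it requires:

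- **FSH and LH, and the other hormone, AFC and egg/embryo endpoints:** the RES minus vitamin E difference with its 95% CI. Where a baseline value is measured, give the difference at 3 months adjusted for that value.
- **Clinical pregnancy:** the risk difference with a 95% CI, with patients with reproductive needs as the stated denominator.
- **Adverse events:** the risk difference with a 95% CI. Here and for pregnancy, use a method suited to small counts; Newcombe is one suitable choice.
- **Interpretation:** a statement that P≥0.05 alone will not be reported as no difference.

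Arm means, SDs and counts can stay alongside. The cost is SAP wording and a little more analysis work, with no new data. The downside is that results will look less certain. The missing rationale for 150 patients is a separate matter that this change does not resolve.
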